1.4.3.2 Itraconazole

In this trial itraconazole will be used in a standard dose of 200 mg once daily for 12 days. Multiple dosing of 200 mg itraconazole up to 15 days was of acceptable tolerability in healthy subjects [[c02336088](#), [c03355329](#), [c08928447](#), [R17-3742](#)].

Proprietary confidential information © 2019 Boehringer Ingelheim International GmbH or one or more of its affiliated companies

In order to address the risk of hepatotoxicity, only subjects with normal liver enzyme values will be included into the study (see Section [3.3.3](#), criterion 23). Safety laboratory parameters will be monitored closely. An individual subject will be removed from the trial if the subject shows an elevation of AST and/or ALT \geq 3-fold ULN combined with an elevation of total bilirubin \geq 2-fold ULN (measured in the same blood sample, see Section [3.3.4.1](#)). Further, most of the reported cases of serious hepatotoxicity during itraconazole treatment occurred in patients that suffered from concomitant liver diseases, had other significant diseases, or took concomitant hepatotoxic drugs. Subjects with liver diseases or a medical history of drug-induced liver failure are excluded from trial participation (Section 3.3.3, criteria 5 and 24).

Itraconazole has shown a dose-related increase in maternal toxicity, embryotoxicity and teratogenicity in nonclinical studies at high doses, and therefore itraconazole must not be used during pregnancy. Women of childbearing potential have to use a highly effective method of contraception until the menstrual period after the last itraconazole dose [[R18-2644](#), [R18-2643](#)]. For risk mitigation, only male subjects will be included into this clinical trial.

Considering these safety measures and taking into account the reported acceptable tolerability of itraconazole, the planned administration of itraconazole does not represent an undue risk to healthy male volunteers.

1.4.3.3 Potential drug-drug interaction between itraconazole and BI 730357

It is likely that concomitant administration of BI 730357 with itraconazole may cause an increase of plasma concentrations and $t_{1/2}$ of BI 730357. The effect of itraconazole in increasing C_{max} and AUC of other drugs can be as high as 3.4-fold and 11-fold, respectively, as seen with oral midazolam, a sensitive CYP3A4 substrate, when co-administered with oral itraconazole 200 mg/d [[R01-0516](#), R18-2644]. Therefore, a low dose of 50 mg BI 730357 has been selected for this trial.

the ratios of gMean plasma exposure parameters at 800 mg and at 50 mg were approximately 14 (C_{max}) and 13 (AUC_{0-24}). These ratios are assessed to be sufficient as safety margins for the current trial, even in case of substantial increases of BI 730357 plasma concentrations by itraconazole as it has been described for midazolam (see above).

1.4.3.4 Drug-induced liver injury

Although rare, a potential for drug-induced liver injury (DILI) is under constant surveillance by sponsors and regulators. Therefore, this trial requires timely detection, evaluation, and follow-up of laboratory alterations in selected liver laboratory parameters to ensure subjects' safety; see also section [5.2.6.1.4](#), adverse events of special interest.

1.4.4 Overall assessment of benefit-risk ratio

BI 730357 is a novel ROR γ t antagonist that has been adequately characterised in pre-clinical studies. The non-clinical safety package supports clinical trials in males and females with administration of BI 730357 for up to 39 weeks.

Preliminary data of the SRD part of trial 1407-0001 indicate good safety and tolerability of single oral doses of BI 730357 at all dose levels, i.e. up to 800 mg (see IB [[c09228382](#)]).

Due to the low dose of BI 730357 selected for this trial, BI 730357 plasma exposures, even in case of a substantial effect of itraconazole, are expected to be well within plasma exposure values that were observed in the SRD part of trial 1407-0001 and that were associated with good safety and tolerability.

The trial design is optimized to collect as much relevant information as possible on the pharmacokinetics of BI 730357 without exposing participating volunteers to undue risk. The potential for side effects has been assessed to be minimal and thus acceptable. However, there is always the potential for subjects receiving medication to experience adverse events (AEs), and rarely also serious adverse events (SAEs). Risks for subjects will be minimized and addressed by eligibility criteria, safety laboratory examinations, ECG and vital sign measurements, in-house observation periods and AE questioning.

Itraconazole is a recommended inhibitor of CYP3A in clinical trials and has been used successfully previously in clinical trials in healthy volunteers. The drug has a potential for hepatotoxicity, which is however accounted for by stringent exclusion criteria, liver enzyme measurement as part of safety laboratory examinations and stopping criteria for the individual subject.

If the investigator should have any clinical concern, the safety of subjects will be of upmost importance. The Investigator has the discretion to remove subjects from the trial should there be any safety concerns, or if the subjects' wellbeing is at jeopardy.

BI 730357 has the potential to have a broader effect in Th17-mediated diseases than individual cytokine blockades alone (e.g., IL-23 or IL-17), thereby filling an unmet medical need for the introduction of new, efficacious oral treatment options in the treatment of psoriasis and other Th17-mediated diseases.

This trial is required for the development of BI 730357. It is designed to assess the *in vivo* victim potential of BI 730357 for CYP3A inhibition. The resulting data are planned to inform concomitant medication restrictions in planned patient trials.

Considering the medical need for an effective and safe treatment of psoriasis, the benefit of this trial is assessed to outweigh the potential risks.

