1.2.3 Residual Effect Period

The Residual Effect Period (REP, i.e., the period after the last dose with measurable drug levels and/or pharmacodynamic effects still likely to be present) of BI 730357 is 7 days for the mono-therapy (Treatment R). When given together with itraconazole (Treatment T), it is expected that plasma exposure of BI 730357 could be increased (albeit within the range explored in the clinical trial 1407-0001), and the time of relevant plasma exposure could be prolonged, which in turn could result in a prolonged period in which adverse effects could potentially occur.

For the use of itraconazole in Treatment T, the REP is defined as 9 days after last administration of itraconazole on Day 9 in Period 2. Therefore, the follow-up period will start earliest on Day 18 following BI 730357 dosing in Period 2, as this is expected to cover the period in which any potential adverse effects could reasonably occur.

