1.3 RATIONALE FOR PERFORMING THE TRIAL

Based on in vitro data, CYP3A is responsible for approximately 90% of the metabolism of BI 730357. Therefore, the DDI victim potential of BI 730357 with regards to CYP3A inhibition is considered high if metabolism is the *main clearance pathway*. Inhibition of CYP3A4 may result in an increased drug exposure which might impact the safety of the patients.

This clinical trial will be performed in order to assess whether and to which extent the kinetics of BI 730357 is affected by the co-administration of a drug that inhibits CYP3A4. The probe drug to test the *in-vivo* inhibition of CYP3A4 is itraconazole.

Itraconazole is chosen for this trial as perpetrator drug, as this drug is recommended as strong inhibitor of CYP3A by EMA [[P15-06991](#)], as strong index inhibitor of CYP3A by FDA [[R18-0241](#)], and as strong inhibitor of CYP3A by PMDA [[P15-06298](#)]. Moreover, safety and tolerability of itraconazole were acceptable in previous drug-drug interaction trials ([c02336088](#), [c03355329](#), [c08928447](#)).

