4.1.2 Selection of doses in the trial

Perpetrator (itraconazole)

The dose of itraconazole selected for this trial reflects standard clinical doses, is considered sufficient to yield significant CYP3A inhibition and has been used successfully and safely in previous drug-drug interaction trials ([c02336088](#), [c03355329](#), [c08928447](#)).

Victim (BI 730357)

Based on *in vitro* data, CYP3A is responsible for approximately 90% of the metabolism of BI 730357. If metabolic clearance is the main pathway of BI 730357 elimination, concomitant administration of BI 730357 with the strong CYP3A inhibitor itraconazole may result in substantial increases of BI 730357 plasma concentrations.

For the current trial, a dose of 50 mg BI 730357 is selected, in order to ensure that BI 730357 plasma concentrations, even in case of a substantial increase when given with itraconazole, are within the range of concentrations that were explored in the SRD part of trial 1407-0001 and that were associated with good safety and tolerability.

In the SRD part of trial 1407-0001, single oral doses of 2 to 800 mg BI 730357 were administered as oral solution or tablet formulation under fasting or fed conditions, and available data indicate that, at all doses tested, BI 730357 administration was safe and well tolerated.

I.e., the ratios of gMean plasma exposure parameters at 800 mg and at 50 mg were approximately 14 (C_{max}) and 13 (AUC_{0-24}). These ratios are assessed to be sufficient as safety margins for the current trial, to cover for increases of BI 730357 plasma exposures when given together with itraconazole (see also section [1.4.3.3](#)).

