4.1.3 Method of assigning subjects to treatment groups

There is only one treatment sequence investigated in this trial, and each subject will be allocated to the same treatment sequence (R-T). The subjects will be allocated to a study subject number by drawing lots prior to first administration of trial medication in the morning of Day 1 of Visit 2. The randomization list of study subject numbers and assigned treatment sequence will be provided to the trial site in advance. Note that the randomization list is just needed for logistical reasons in this non-randomized, open-label trial. Hence, no bias is introduced when providing the randomization list in advance to the site. Reference and test treatments will be administered in the sequence specified in the [Flow Chart](#).

Once a subject number has been assigned, it cannot be reassigned to any other subject.

All subjects may be treated in one cohort, i.e. all subjects may receive treatment on the same calendar day. In case this is not feasible (e.g., due to logistical or recruitment reasons), the group may be split into several cohorts as required. Treatment of all subjects on the same calendar day is acceptable (for safety margin to exposure reached in previous SRD trial 1407.1 refer to Section 1.4.3.3; for discussion of study-associated risks and safety measures see Section [1.4.3](#)).

The randomisation procedure is described in Section [7.6](#).

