7.7 DETERMINATION OF SAMPLE SIZE

It is planned to enter a total of 14 subjects in the trial, accounting for up to 2 non PK evaluable subjects. The planned sample size is not based on a power calculation but is considered sufficient to achieve the aims of this exploratory trial. With this sample size, the following precision in estimating the ratio of geometric means (test/reference) can be expected with 95% probability. Precision is defined as the ratio of upper CI limit to the relative BA estimate. Note that the precision is independent of the actual ratio of geometric means.

The intra-individual coefficient of variation (gCV) is estimated from inter-individual gCV from pharmacokinetic data of the SRD part of a previous trial (Study 1407-0001) using the result of 50 mg dose. The observed inter-individual gCV was 41.9% for C_{max} and 51.5% for AUC_{0-tz}. Assuming a within-subject correlation of 0.6 for C_{max} and 0.8 for AUC_{0-tz}, the estimated intra-individual gCV will roughly be 26% for C_{max} and 22% for AUC_{0-tz}.

Assuming a gCV of 22% for BI 730357 and given a sample size of 12 subjects with evaluable data for primary analysis, the precision of the two-sided 90% confidence interval of the bioavailability ratio will be approximately 1.238, for a greater gCV of 26%, the precision would still be approximately 1.285. Table [7.7: 1](#) provides an overview of the achievable

Proprietary confidential information © 2019 Boehringer Ingelheim International GmbH or one or more of its affiliated companies

precision for estimating the ratio of geometric means (test/reference). For illustrative purposes, the expected 90% confidence intervals with 95% tolerance probability are displayed for different values of the ratios T/R of geometric means.

Table 7.7: 1 Precision that can be expected with 95% tolerance probability and illustrative two-sided 90% confidence intervals around the ratios of geometric means (T/R) for different gCVs in a one-way crossover trial (N=12)

gCV [%]	Precision upper CL / relative BA estimate	Ratio [%] [*]	Lower CL [%]	Upper CL [%]
22	1.238	50	40.40	61.88
22	1.238	100	80.80	123.76
22	1.238	150	121.20	185.64
22	1.238	200	161.60	247.52
26	1.285	50	38.91	64.25
26	1.285	100	77.82	128.50
26	1.285	150	116.73	192.75
26	1.285	200	155.64	257.01

^{*}Ratio of geometric means (test/reference) for a PK endpoint is defined by $\exp(\mu_T)/\exp(\mu_R)$.

The expected 90% confidence interval limits in the table were derived by

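### Is it fair to call exposure under itraconazole well inside the earlier range when the protocol's own benchmark leaves an AUC margin of only about 1.2?

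*Protocol*

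**What the plan says.** Protocol Section 1.4.3.3 notes that itraconazole's effect on Cmax and AUC of other drugs "can be as high as 3.4-fold and 11-fold, respectively, as seen with oral midazolam, a sensitive CYP3A4 substrate". It then gives the ratios of geometric-mean exposure at 800 mg to that at 50 mg in the single-rising-dose trial: about 14 for Cmax and about 13 for AUC0-24. On these it concludes: "These ratios are assessed to be sufficient as safety margins for the current trial, even in case of substantial increases", and it names midazolam as the example of such an increase.

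The conclusion is repeated with different strength elsewhere:

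- Section 1.2.3: exposure "could be increased (albeit within the range explored in the clinical trial 1407-0001), and the time of relevant plasma exposure could be prolonged".
- Section 4.1.2: concentrations under itraconazole "are within the range of concentrations that were explored in the SRD part of trial 1407-0001".
- Section 1.4.4: exposures "are expected to be well within plasma exposure values that were observed in the SRD part of trial 1407-0001".

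Section 4.1.3 cites the Section 1.4.3.3 margin when it accepts dosing all subjects on one calendar day. No visible text states the margin that remains after the benchmark increase, for either parameter.

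**The concern.** The ratios of 14 and 13 look alike, so one joint verdict seems natural. The benchmark increases they must absorb are very different, 3.4 and 11. After division the Cmax margin is wide and the AUC margin is thin, yet Section 1.4.4 uses its strongest wording for both. The AUC margin is also smaller than one between-subject standard deviation, so a subject with above-average exposure could pass the 800 mg geometric mean.

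Two further features sharpen the point. The protocol says that in vitro "CYP3A is responsible for approximately 90% of the metabolism of BI 730357", so a large effect is not far-fetched if metabolism dominates clearance. And the 13 covers only the first 24 hours, while Section 1.2.3 expects prolonged exposure and the Flow Chart extends sampling from 167 h in Period 1 to 263 h in Period 2. The dose rationale and the benefit-risk statement both lean on this reasoning, so an overstated margin in a safety argument deserves a check.

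**Working it through.** **Inputs.** From Section 1.4.3.3: 800/50 mg geometric-mean ratios of 14 (Cmax) and 13 (AUC0-24), and midazolam increases of 3.4 (Cmax) and 11 (AUC, interval not stated). From Section 7.7: "The observed inter-individual gCV was 41.9% for" Cmax and 51.5% for AUC0-tz, both at 50 mg. The 14 and 13 cannot be rebuilt because the underlying means are not in the public text. They are plausible against the dose ratio 800/50 = 16 (14/16 = 0.88; 13/16 = 0.81).

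**Step 1: margin between geometric means** = (800/50 mg ratio) / (fold-increase).

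- Cmax: 14/3.4 = 4.12; projected mean is 3.4/14 = 24% of the 800 mg mean.
- AUC: 13/11 = 1.18; projected mean is 11/13 = 85% of the 800 mg mean.

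If all four printed figures are rounded, the margins range from 3.9 to 4.3 and from 1.09 to 1.29. Both stay above 1.

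**Step 2: AUC margin at other effect sizes** (13 / fold-increase).

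| Fold-increase | Margin | Share of 800 mg mean |
|---|---|---|
| 11 | 1.18 | 85% |
| 10 | 1.30 | 77% |
| 8 | 1.63 | 62% |
| 5 | 2.6 | 38% |
| 3 | 4.3 | 23% |

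The 10-fold row is the ceiling 1/(1 − 0.9), assuming that all clearance is metabolic, CYP3A is fully blocked and first-pass effects are ignored.

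**Step 3: between-subject spread.** Log-scale SD = sqrt(ln(1 + gCV²)).

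- Cmax: sqrt(ln(1 + 0.419²)) = 0.402. Margin in SDs: ln(4.12)/0.402 = 3.5.
- AUC: sqrt(ln(1 + 0.515²)) = 0.485, a factor of 1.62. Margin in SDs: ln(1.18)/0.485 = 0.34.

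The AUC margin is below one SD only for effects above 13/1.62 = 8-fold.

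**Step 4: which comparison tests the sentence.** Assume log-normal exposure, the 51.5% gCV for AUC and the same spread in both groups. At 11-fold:

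- Subjects above the 800 mg geometric mean AUC: 1 − Φ(0.34) = 37%, about 5 of 14.
- Subjects above the 95th percentile of AUC at 800 mg: 1 − Φ(0.34 + 1.645) = 2.3%.

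The first figure compares a spread-out group with the centre of the other group. By definition, about half of the 800 mg subjects lie above that centre as well. Section 1.4.4 refers to values that were observed, so the second figure is closer to what it claims.

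**Step 5: are 13 and 11 the same measure?** AUC0-24 cannot exceed 24 h × Cmax. If Cmax rises 3.4-fold and AUC0-24 rises 11-fold, the mean concentration over 0–24 h without itraconazole must be at most 3.4/11 = 31% of Cmax. Whether BI 730357 meets this is not visible. Sampling to 167 h and a 7-day residual effect period suggest slow elimination, which makes it uncertain. So 1.18 is the low end for AUC0-24, not a firm estimate.

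**The case for a change.** The strongest case for a change is that the benchmark is the protocol's own, the division is elementary, and a single verdict covers margins of 4.1 and 1.2. Section 1.4.4 is also worded more strongly than Sections 1.2.3 and 4.1.2. All of that is correct, and for AUC in the midazolam case the stronger phrase is generous.

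The interval point also stands in part. No 800/50 mg ratio for total AUC is visible. If it were below 11, which is 11/16 = 69% of dose-proportional against 81% for AUC0-24, an 11-fold rise in total AUC would carry the mean past the 800 mg mean. The public text cannot settle this. It is also visibly cut at the places where the answer would be expected: Sections 1.2.1.2.1 (clinical pharmacokinetics) and 1.2.1.2.2 (clinical safety) are nearly empty, and the sentence giving the ratios in Section 1.4.3.3 begins mid-way. What is missing for that reason cannot be held against the plan.

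The rest carries less weight. The 0.34 SD figure, and the statement that a subject one SD high would reach 11 × 1.62/13 = 1.37 times the 800 mg mean, apply spread to one group only. Eleven-fold is an upper benchmark from a sensitive substrate, and Sections 1.3 and 4.1.2 make a large effect conditional on metabolism being the main clearance route. Same-day dosing in Section 4.1.3 rests on Section 1.4.3.3 and the risk discussion in Section 1.4.3, not on the wording of Section 1.4.4. The protocol reports 800 mg as well tolerated, not as a toxicity limit.

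**Conclusion.** No change is needed. No printed figure is wrong. On geometric means, sufficiency (Section 1.4.3.3) and staying within range (Sections 1.2.3 and 4.1.2) hold even at the benchmark: 24% of the 800 mg mean for Cmax and 85% for AUC. What remains is one phrase in Section 1.4.4 that suits Cmax (margin 4.1) better than AUC (margin about 1.2, or 1.09 to 1.29 with rounding) in the upper case. At 5-fold the AUC margin is already 2.6.

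A revision would only display a division of four numbers that Section 1.4.3.3 prints together. It would alter no procedure, endpoint, analysis or conclusion. The expected prolongation is acknowledged in Section 1.2.3, with follow-up starting no earlier than Day 18 and sampling to 263 h.

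This rests on treating the 11-fold figure as comparable with AUC0-24 and, for the 2% figure, on log-normal exposure with a 51.5% gCV in both groups. The individual 800 mg values that would test the phrase directly are not in the public text.

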2. TRIAL OBJECTIVES AND ENDPOINTS

2.1 MAIN OBJECTIVES, PRIMARY AND SECONDARY ENDPOINTS

2.1.1 Main objectives

The main objective of this trial is to investigate the relative bioavailability of BI 730357 in plasma when given as oral single dose together with multiple oral doses of itraconazole (Test, T) as compared to when given alone as oral single dose (Reference, R).

2.1.2 Primary endpoints

The following pharmacokinetic parameters will be determined for BI 730357:

- AUC_{0-tz} (area under the concentration-time curve of the analyte in plasma over the time interval from 0 to the last quantifiable data point)
- C_{max} (maximum measured concentration of the analyte in plasma)

2.1.3 Secondary endpoint

The following pharmacokinetic parameter will be determined for BI 730357:

- $AUC_{0-\infty}$ (area under the concentration-time curve of the analyte in plasma over the time interval from 0 extrapolated to infinity)

2.2.2.2 Safety and tolerability

Safety and tolerability of BI 730357 and itraconazole will be assessed based on:

- Adverse events (including clinically relevant findings from the physical examination)
- Safety laboratory tests
- 12-lead ECG
- Vital signs (blood pressure, pulse rate)

3. DESCRIPTION OF DESIGN AND TRIAL POPULATION

3.1 OVERALL TRIAL DESIGN AND PLAN

The study will be performed as an open-label, two-treatment, two-period, one-way crossover trial in healthy male subjects in order to compare the test treatment (T) to the reference treatment (R). The treatments will be one oral single dose of 50 mg BI 730357 as tablet formulation (tablet strength: 50 mg) together with multiple oral doses of 200 mg itraconazole as oral solution formulation (concentration: 10 mg/mL) (T) and one oral single dose of 50 mg BI 730357 as tablet formulation (tablet strength: 50 mg) given alone (R). In both treatments, BI 730357 is administered to subjects in the fasting state. In the first treatment period (Period 1, Visit 2), all subjects are planned to undergo treatment R, and in the second treatment period (Period 2, Visit 3), all subjects are planned to undergo treatment T. For details, refer to Section [4.1](#).

There will be a washout interval of at least 10 days between the administrations of BI 730357.

An overview of all relevant trial activities is provided in the [Flow Chart](#). For visit schedule and details of trial procedures at selected visits, refer to Sections [6.1](#) and [6.2](#), respectively.

3.2 DISCUSSION OF TRIAL DESIGN, INCLUDING THE CHOICE OF CONTROL GROUP

For relative bioavailability trials, the crossover design is preferred because of its efficiency: since each subject serves as his own control, the comparison between treatments is based on an intra-subject comparison, thus removing inter-subject variability from the comparison between treatments [\[R94-1529\]](#).

Because of the long half-life of itraconazole (about 40 hours) and its metabolites, a one-way crossover design was selected, with administration of itraconazole in the second study period only. This design is not expected to lead to systematic errors in the estimation of the treatment effects since nonspecific time-effects are unlikely due to the short trial duration. For itraconazole studies, this design is recommended by the Innovation and Quality in Pharmaceutical Development's Clinical Pharmacology Leadership Group (CPLG) [\[R17-3744\]](#).

For this pharmacokinetic drug-drug interaction trial, open-label treatment is acceptable, because the primary and secondary endpoints of this trial are pharmacokinetic endpoints derived from measurement of plasma concentrations of BI 730357. These endpoints are not expected to be affected by knowledge of treatment.

